
**The following documents are currently attached to this item:**

*There are no documents attached for this item.*

## **Data confidentiality**

- Paper-based records will be kept in a secure location and only be accessible to personnel involved in the study.**
- Computer-based files will only be made available to personnel involved in the study through the use of access privileges and passwords.**
- Prior to access to any study-related information, personnel will be required to sign statements agreeing to protect the security and confidentiality of identifiable information.**
- Wherever feasible, identifiers will be removed from study-related information.**

**A Certificate of Confidentiality will be obtained, because the research could place the subject at risk of criminal or civil liability or cause damage to the subject's financial standing, employability, or liability.**

**A waiver of documentation of consent is being requested, because the only link between the subject and the study would be the consent document and the primary risk is a breach of confidentiality. (This is not an option for FDA-regulated research.)**

**Precautions are in place to ensure the data is secure by using passwords and encryption, because the research involves web-based surveys.**

**Audio and/or video recordings will be transcribed and then destroyed to eliminate audible identification of subjects.**

## **Subject Confidentiality**

All research information will be kept in locked cabinets, in secure locked offices at the School of Nursing. Access to identifying information will be limited to research staff assigned to the project. Subjects will be advised of the precautions we will take to preserve confidentiality during the consent process. Data with identifiers will not be permitted outside of the PI office space. All discussions between the research staff members will be held in a private area. Pre-coded data collection instruments will be prepared for use with study participants at each testing occasion. Identification numbers to assure participant confidentiality will be used. Only one master log of subject name, address and telephone number and study identification assignment will be maintained. This log, in both hard copy and disk, will be stored in a locked filing cabinet separate from other identifying information. All de-identified data abstracted from study tools will be entered into a password protected and encrypted internet-based data management system known as REDCap (Research Electronic Data Capture). We will store all paper-based records in the PI's secure office space for 7 years, per requirements, and only de-identified data (without names or medical record numbers of patients enrolled) will be entered into REDCap system.

## **Sensitive Research Information\***

Does this research involve collection of sensitive information about the subjects that should be excluded from the electronic medical record?

No

## **Subject Privacy**

Privacy refers to the person's desire to control access of others to themselves. Privacy concerns people, whereas confidentiality concerns data. Describe the strategies to protect privacy giving consideration to the following: The degree to which privacy can be expected in the proposed research and the safeguards that will be put into place to respect those boundaries. The methods used to identify and contact potential participants. The settings in which an individual will be interacting with an investigator. The privacy guidelines developed by relevant professions, professional associations and scholarly disciplines (e.g., psychiatry, genetic counseling, oral history, anthropology, psychology).

We will only contact individuals who have given previous permission to be contacted for research, or who call or contact the research team to express interest in the study. Those individuals who express interest in the study will receive a telephone call to describe the study, and conduct a telephone screen. Once an individual is screened, a copy of the consent form will be mailed, and a home visit will be scheduled to conduct the consent and baseline visit.

**Data Disclosure**

Will the data be disclosed to anyone who is not listed under Personnel?

No

**Data Protection\***

- Name**
- Street address, city, county, precinct, zip code, and equivalent geocodes**
  - All elements of dates (except year) for dates directly related to an individual and all ages over 89**
- Telephone and fax number**
  - Electronic mail addresses**
  - Social security numbers**
  - Medical record numbers**
  - Health plan ID numbers**
  - Account numbers**
  - Certificate/license numbers**
  - Vehicle identifiers and serial numbers, including license plate numbers**
  - Device identifiers/serial numbers**
  - Web addresses (URLs)**
  - Internet IP addresses**
  - Biometric identifiers, incl. finger and voice prints**
  - Full face photographic images and any comparable images**
  - Any other unique identifying number, characteristic, or code**
  - None**

Does your research request both a waiver of HIPAA authorization for collection of patient information and involve providing Protected Health Information ("PHI") that is classified as a "limited data set" (city/town/state/zip code, dates except year, ages less than 90 or aggregate report for over 90) to a recipient outside of the University of Pennsylvania covered entity?

No

**Tissue Specimens Obtained as Part of Research\***

Are Tissue Specimens being obtained for research?

No

**Tissue Specimens - Collected during regular care\***

Will tissue specimens be collected during regular clinical care (for treatment or diagnosis)?

No

**Tissue Specimens - otherwise discarded\***

Would specimens otherwise be discarded?

No

**Tissue Specimens - publicly available\***

Will tissue specimens be publicly available?

No

**Tissue Specimens - Collected as part of research protocol\***

Will tissue specimens be collected as part of the research protocol?

No

**Tissue Specimens - Banking of blood, tissue etc. for future use\***

Does research involve banking of blood, tissue, etc. for future use?

No

## **Genetic testing**

If genetic testing is involved, describe the nature of the tests, including if the testing is predictive or exploratory in nature. If predictive, please describe plan for disclosing results to subjects and provision of genetic counseling. Describe how subject confidentiality will be protected Note: If no genetic testing is to be obtained, write: "Not applicable."

Not applicable

# **Consent**

## **1. Consent Process**

### **Overview**

Two groups of individuals will be participants in this research study i.e. primary participants--Persons with Dementia (PWD), their informal caregivers (CG). We will recruit participants through flyers. The flyers will have contact information for interested patients to contact the research staff. The research staff will call interested potential participants. Research staff will not obtain names of potential participants or their contact information until they have expressed a willingness to participate. Enrollment involves a 2-step screening process; an initial telephone screen with CGs followed by a clinical home assessment to confirm PWD diagnosis, and inclusion criteria. **TELEPHONE SCREENING ASSENT:** First, CGs contacting the research team are screened to determine initial potential eligibility using a 10 minute telephone screen tested in our pilot phase. Also, CGs will be asked about symptoms of CRD. The presence of one or more symptoms occurring in the PWD several times a week over the past month will be used as the cut off for potential eligibility. These criteria will maximize the number of individuals who are eligible in the clinical home screening stage. Assent for telephone screen (based on an IRB approved telephone screening form and interviewer script) will be obtained from PWD during the initial phone screen by a trained study coordinator or research assistant. If PWDs cognitive impairment prevents him/her from accurately recounting the purpose of the screen immediately following the description, the interviewer will ask to speak with the legal authorized representative (LAR), usually the CG, to obtain proxy phone screening assent. PWD and CGs will be informed that their participation in the telephone interview is confidential and completely voluntary. The objectives, procedures, and a clear statement explaining risks and benefits of this study will be presented at the telephone screen (see uploaded telephone screen). **WRITTEN CONSENT:** CGs screened potentially eligible by telephone and willing to participate will then be scheduled to receive a home assessment and consent visit by [name] or study nurse within a 10 day window and who will conduct a structured and standard clinical examination to: 1) obtain history of cognitive function and cognitive decline, pattern of losses, behavioral changes, and current functioning; 2) substantiate dementia diagnosis and disease stage using standardized mental, general physical, and neurological examinations including the Clinical Dementia Rating Scale (CDR-0.5=very mild dementia; CDR-1=mild; CDR-2=moderate; CDR-3=severe), 3) obtain medical history, co-morbidities, and medication use; and 4) establish presence of CRD. We will mail consent forms out to PWD and CGs immediately following a positive telephone screen so they have some time to review the form prior to the in-person written consent procedures. Written consent will be obtained for both the PWD and their CG at the beginning of the in-home visit. The consent form, written in large print, will assure participants that their participation is voluntary. The consent will explain to them in laymans terms that they will wear an activity monitoring device on their wrist. The consent form will inform them that we will be collecting a small amount of saliva and ask them to complete a brief questionnaires to provide information about their medical conditions. The consent form will also inform them that they will be randomly assigned to one of two groups. It will inform them of all aspects of the study and their right to withdraw at any time. We will follow similar procedures as used in the pilot study for the consenting process. Every reasonable effort will be made to ensure that participants with sensory deficits have access to any and all medical devices and aides (e.g. reading glasses, hearing aides with functioning battery) during the consent procedure and during study visits. For those with language deficits, every reasonable attempt will be made ensure adequate communication. The consent designee will have the discretion to terminate the interview if he/she believes that communication is too impaired to ensure proper consent procedures. If the PWD is too impaired to provide consent, proxy consent will be obtained from the legally authorized representative (LAR), and oral assent will be obtained from the PWD. PWD and their CGs will receive an explicit assessment of capacity and the consent procedure

will be documented by the study's consent designee. [name] will train and very closely supervise the study team in conducting the consent procedures and capacity assessment and ensure that all ethical procedures are followed and are documented. She has extensive experience performing the consent procedures in vulnerable participants who suffer from cognitive impairment. For primary participants and caregiver, who may be at risk for diminished decision making capacity, consent designees will conduct an explicit assessment of capacity to consent.

### **Children and Adolescents**

N/A

### **Adult Subjects Not Competent to Give Consent**

Individuals with dementia in this study are expected to have progressive decisional impairment. As such, the subject will be asked to involve an individual of his/her choice at the beginning of the study who may later serve as an LAR. Capacity to provide informed consent will be determined by asking standard reflective questions throughout the consent process. 1) What is the main purpose of the study? 2) What are the benefits of the study? 3) What are the risks of the study? 4) Are you able to withdraw from the study at any time? If a person with suspected dementia is unable to answer the question the first time the research team member will review the section of the consent and ask the question a second time. If at any point the person with dementia is unable to answer the question correctly after reviewing the section then proxy consent will be sought. If the person with dementia is unable to provide informed consent then his/her signed or verbal assent will be sought. The subject's assent will be obtained after informing the subject of the following: 1. The fact that he/she is being asked to participate in research 2. That he/she has been determined to lack capacity to self-consent to research participation 3. The name of the LAR who has been identified, that he or she has granted permission for the subject's participation in the research and the extent to which the LAR will be involved in the subject's research participation 4. That the subject may choose freely to undergo study procedures or may withdraw from participation at any time without penalty or loss of benefits. At each study visit the study team member will refresh the subjects of the major objectives of the study, the scope of his/her participation, and the fact that participation is voluntary.

## **2. Waiver of Consent**

### **Waiver or Alteration of Informed Consent\***

No Waiver Requested

### **Minimal Risk\***

### **Impact on Subject Rights and Welfare\***

### **Waiver Essential to Research\***

### **Additional Information to Subjects**

### **Written Statement of Research\***

No

**If no written statement will be provided, please provide justification**

**The following documents are currently attached to this item:**

*There are no documents attached for this item.*

## **Risk / Benefit**

### **Potential Study Risks**

The risks of participation should be no more than minimal with effective confidentiality safeguards. Should confidentiality safeguards fail, there is potentially significant harm in the form of social risks and disclosure of private information. The safeguards to prevent inadvertent disclosure of study data are described in the section below. Some participants might find it somewhat uncomfortable to wear an

actigraph for multiple 24-hour periods.

### **Potential Study Benefits**

Caregivers in the experimental group will potentially benefit from the intervention by learning specific techniques for tailoring and timing activities that engage PWD and utilize their preserved capabilities. PWD will potentially benefit from the intervention since it is designed to reduce their sleep disruption and symptoms of CRD and enhance their quality of life by introducing activities that they are able to participate in and which they find meaningful. They should also benefit from the potential of reducing caregiver stress and improving their skills in managing difficult behaviors. Participants in the control intervention group may potentially benefit from obtaining important education to address various concerns associated with managing the disease including safety risk. PWD in this group may also benefit by interacting with a staff member trained to engage the person in conversation

### **Alternatives to Participation (optional)**

#### **Data and Safety Monitoring**

The PI will serve as the primary monitor for this study. Plan for reporting unanticipated problems or study deviations. The entire study team will be trained on immediately reporting any adverse events, alerts (e.g., hazardous or emergency situations), or study deviations to the PI. See Chart A (uploaded) for types of possible alerts that may be encountered and types of actions to be taken. If any serious possible or potentially study-related adverse events arise, the PI will notify to the IRB within 48 hours of learning of the events and will provide a safety report describing the adverse event and actions taken by the study. Additionally the PI will keep a log of adverse events in compliance with IRB policies and whether the event is unrelated, possibly related, or probably related to the study or intervention. Study deviations will be reported to the IRB when discovered along with any corrective actions taken by the study. Routine adverse events (such as non-intervention related events such as death) will be summarized for the IRB during the annual reviews. At the start of the study, participants and study partners will be instructed to report serious adverse events to the Coordinator who in turn will notify the PI. Serious adverse events, discovered either by the clinical team in routine activities or ones which the family report, will be presented to the PI together with the available data, and they will make a determination as to whether the event is unrelated, possibly related, or probably related to the study intervention. Because this is an evidence-based psychosocial intervention which seeks to provide care to meet the care needs of individuals with dementia living in the community, we do not anticipate adverse events beyond the background rate for this elderly population. Additionally, the aforementioned terms will be acknowledged if funding is received for a diversity supplement.

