### **Study duration**

The study is estimated to begin in June 2016 and end in May 2021. Each participant will be enrolled in the study for 4 months.

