
morning and evening activities into daily schedule and will provide written instruction on environmental cues to promote activity and sleep. Session 6 (home visit) is a final review session and wrap up. Attention-Control Condition: The attention control group protocol will be delivered by trained RAs who will provide social attention, empathy and engagement similar in duration to that provided to the Timed Activity Intervention group. The length of time spent will be comparable to the length of time spent in the treatment arm, however this condition will contain no active elements beyond its nonspecific components, and no theoretical basis to support an effect on CRDs. The attention-control group will also involve 4 in-home visits in mid morning and up to 4 brief telephone education sessions in the evening. Each session is prescriptive and designed to maximize attention; yet, sessions will not involve any of the components of the timed planned activity (e.g. meaningful activities or relaxation). The attention control group will receive printed Alzheimers Association and NIH materials on home modification, health promotion/ talking to your doctor and advanced care planning that coincide with session content. In Session 1 (home visit), the attention control interventionist will explain the nature of the visit and provides information on home safety. In Sessions 2-3 (one home visit and one phone call) the interventionist will work together with CG to answer questions about home safety and review health promotion material. In Sessions 4-5 (one home visit and one phone call), the interventionist will provide and review information on advanced care planning. Session 6 is a wrap up and review provided in the home. Time with the attention-control RA will be documented on a tracking sheet for each session and signed by the CG. Bi-monthly supervisory sessions with attention-control RAs will involve case presentations to track content of the attention-control sessions. In our previous studies, we found that the attention-control intervention is well received and that participants fully participated in sessions. Treatment Implementation Monitoring: We have a well-defined oversight plan of treatment implementation in both treatment and attention control group arms using the NIH Behavior Change Consortium. To enhance fidelity, we incorporate their recommended strategies including use of treatment manuals, regular contact of PI with interventionists who present cases and discuss protocol issues, and on-going monitoring through direct observation of randomly selected sessions. We will address fidelity through training (using intervention manuals and separate interventionists for each condition), delivery (reminder calls to CGs the night before the intervention sessions, records of home sessions by date and duration, receipt (checklist completed by study team regarding intervention engagement) and enactment (demonstration by CG to interventionists). Feedback will be provided to each interventionist throughout the study period. We will quantitatively evaluate treatment delivery, including dose, intensity; and treatment receipt. Biweekly supervisory sessions will be held with treatment interventionists and control group interventionists separately. All project staff will undergo extensive training before they have contact with subjects. We will audiotape 10% of treatment and 10% of control group sessions. Audiotapes will be reviewed by the research team using monitoring checklists that evaluate quality of the session. Table 1 (uploaded) describes the variables to be measured their respective testing occasions and sources.

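### Death is the plan's example of a routine event for annual summary, so a death can be routed by category before relatedness is judged, and no comparison of events by arm is planned

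*Combined protocol and SAP*

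**What the plan says.** All of the reporting rules are in Data and Safety Monitoring. The PI is the primary monitor. Staff are trained to report any adverse event to the PI at once, and the PI keeps a log that classes each event on a three-level relatedness scale.

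Two routes to the IRB follow.

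- **Expedited:** "If any serious possible or potentially study-related adverse events arise, the PI will notify to the IRB within 48 hours". Serious events, whether found by staff or reported by families, "will be presented to the PI together with the available data", after which "they will make a determination as to whether the event is unrelated, possibly related, or probably related to the study intervention".
- **Annual:** "Routine adverse events (such as non-intervention related events such as death) will be summarized for the IRB during the annual reviews".

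The section closes by expecting no more events than is usual in an elderly population. It gives no figure for that usual rate. The Analysis Plan covers baseline comparability, the efficacy outcomes and mediation, and contains no tabulation of adverse events.

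**The concern.** A death is normally the clearest case of a serious event, and the section's serious-event rule would have it judged individually. The annual-summary sentence instead uses death as its illustration of an event that is both routine and unrelated to the intervention. If staff read that sentence as a category rule, relatedness is settled by the type of event and not by its circumstances, and the IRB hears of it at the next annual review.

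The second strand is that relatedness, judged case by case, is the only way the plan classifies harms. In an elderly population with dementia, most deaths and hospital admissions look like background when taken singly. A difference between arms shows only when all events are counted by arm, whatever their attribution. The trial has a randomised control group that would allow this, but the plan does not ask for it.

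**Working it through.** The plan has no safety figure to reproduce, so this is a check of the text.

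**Step 1: which route does a death take?**

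| State of the case | Serious-event sentences | Annual-summary sentence |
|---|---|---|
| Judged unrelated | No 48-hour report required | Annual summary |
| Judged possibly or probably related | IRB within 48 hours | Does not apply, unless death is treated as unrelated by type |
| Not yet judged | Present to the PI and determine relatedness | Annual summary, if death is treated as unrelated by type |

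The rules agree in the first row. They can diverge in the other two, and the third row matters most because that is where every death starts. Serious and routine are not defined in the visible text, and nothing says that a determination must come before assignment to a route.

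**Step 2: what does the divergence cost?** The expedited route takes 48 hours. An annual summary can come up to about 12 months after the event. On the participant's own schedule, "Each participant will be enrolled in the study for 4 months", so the longest wait is 12 / 4 = 3 full periods of participation.

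**Step 3: who makes the determination, and with what knowledge?**

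- Data and Safety Monitoring has events presented to the PI, then uses a plural pronoun for whoever decides. It is unclear whether this is the PI alone or the PI with others.
- Data Management places the master list, which may carry control or experimental group designations, on the PI's server and in the PI's office.
- Procedures, under treatment implementation monitoring, provides for "regular contact of PI with interventionists who present cases and discuss protocol issues". Each condition has its own interventionists, so hearing a case would usually reveal the arm.
- Masking is described for data collectors (Method for Assigning Subjects to Groups) and for outcome interviewers (Administration of Surveys and/or Process; Procedures). It is not described for the PI.

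Access to assignment is therefore stated, and knowledge of it is a strong inference. No masked or independent reviewer of events is named.

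**Step 4: can the stated safety expectation be checked?** It needs either an external rate or a comparison between arms. Neither Data and Safety Monitoring nor the Analysis Plan supplies one. The nearest item is the planned look at how dropouts affect group balance. That could bring deaths in as dropouts, but not as a count of safety events by arm.

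**The case against.** The strongest reply is that the annual route is limited to events unrelated to the intervention, which presupposes that someone has judged them so. Read with the log and the serious-event sentences, the order would be report, judge, then route, and nothing would conflict. That reading is reasonable and may be what was meant. It is not what is written, and a reporting rule should not depend on staff choosing it.

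Other objections stand, and they limit the point.

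- **A reader might infer that deaths escape review altogether.** They do not. Every adverse event goes to the PI at once and into a log that records relatedness, with no exception for death. What can be missed is the 48-hour IRB report and, if the category is applied by default, a case-specific judgement.
- **A reader might infer that the trial's safety conclusion rests on unmasked attribution.** The plan specifies no safety conclusion, and attribution governs the reporting route only. The PI's masking status is nowhere stated.
- **A reader might infer that control-arm events will be dismissed, because "this condition will contain no active elements beyond its nonspecific components".** That text concerns efficacy: its sentence goes on to deny a theoretical basis for an effect on circadian symptoms. The log also allows an event to be related to the study as well as to the intervention. And if control events were preferentially called unrelated, an experimental-arm excess of related events would be exaggerated, not hidden.
- **Some governing material is not visible.** The uploaded chart of alerts and actions, and the IRB policies the log must follow, may define terms. They cannot be assumed silent, but they would not change the wording of the death sentence.
- **The study is described as minimal risk.** This argues for a light remedy, but not for leaving two routes unreconciled.

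**Conclusion.** The point holds in a limited form. The two reporting routes overlap for deaths, the text does not say which governs, and a death can be assigned to annual summary by category. Separately, the only classification of harms described is attribution by a PI with access to group assignment, and no count by arm regardless of attribution is planned.

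The demonstrable size is the difference between 48 hours and up to about 12 months in notifying the IRB of a death that should have been expedited. It is tempting to turn this into a number of further dyads randomised during the delay, but the reported status does not support that. The modification form gives 170 enrolled against a target of 200, so at most 200 - 170 = 30 remain, with 0 in intervention and 35 in follow-up. Prompt routing therefore has less left to affect, while the table by arm would cover every event so far.

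The documents give no number of deaths and no background rate, so nothing here suggests that an imbalance exists. The conclusion assumes that the attachments not shown do not already require a determination before routing. Neither the efficacy analysis nor the sample size is affected.

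**What to change.** 1. In Data and Safety Monitoring, reconcile the two routes. Remove death as the example of a routine event. State that every death and every serious event receives a documented relatedness determination before it is assigned to the 48-hour or the annual route.
2. Say who makes the determination, and have it made from an event summary that omits the arm where feasible.
3. In the Analysis Plan, add a descriptive table for the final report: all deaths and serious events by randomised arm, regardless of attribution, with the number randomised to each arm as denominator. The existing log and the group designations on the master list should supply it.

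The cost is a wording change, a short arm-free summary per event and one table. A few more determinations must be documented, and the arm cannot always be concealed, for example when an event happens during an intervention activity. Treatment, visits and trial size do not change.
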